4.6.2. Analyses of Primary Efficacy Endpoint

The primary analysis for the efficacy endpoints will be based on the mITT population.

The following null hypothesis (H0) and alternative hypothesis (H1) will be tested for each KPL-404 dose against placebo:

- H0: No treatment difference between KPL-404 and placebo.
- H1: There is a treatment difference between KPL-404 and placebo.

The primary estimand for the primary endpoint is defined in Table 1, using the hypothetical strategy.

The intercurrent event that is deemed to have an impact on the interpretation of the variable of interest is treatment discontinuation or using any rescue medications. Data will be set to missing values after occurrence of any intercurrent event prior to Week 12, and the subject's last post baseline observation before the intercurrent event will be carried forward (LOCF) to impute missing endpoint value (for subjects whose postbaseline values are all missing, the baseline will be used to impute). Missing data at Week 12 will be imputed with LOCF method. Analysis of covariance (ANCOVA) models will be used to compare the change from baseline in DAS28-CRP at Week 12 for each of the KPL-404 dose groups and placebo. Baseline value and stratification factor will be included as covariates in the ANCOVA model. The least square (LS) mean of each treatment group, LS mean differences (each KPL-404 group vs. placebo), their standard errors and two-sided 95% CIs, and the nominal p-values for treatment differences will be obtained from the model. No testing between the two KPL-404 dose groups will be conducted.

Sensitivity Analysis (As-Observed Analysis)

The data collected after the intercurrent event will be included in the sensitivity analysis to evaluate the robustness of the primary analysis results with respect to the method of handling data while treatment discontinuation or taking the rescue medications (treatment policy strategy). In addition, for subjects discontinuing the study treatment before Week 12, their off-study treatment values measured up to Week 12 will be included in the analysis. There is no imputation for missing data at Week 12.

For the sensitivity analysis of the primary efficacy endpoint, the observed data will be analyzed using a mixed model for repeated measures (MMRM) under the missing-at-random (MAR) assumption. Under this assumption, the efficacy outcome of subjects in each treatment group after early discontinuation will exhibit the same future evolution as subjects in the same group remaining in the study. The MMRM model will include fixed factors for treatment, visit, stratification factor, and treatment-by-visit interaction, and baseline DAS28-CRP as a covariate. An unstructured covariance matrix will be used to model the within-subject correlation. Kenward-Roger approximation will be used to calculate the denominator degrees of freedom. The LS mean, standard error, and LS mean treatment difference, along with the 95% CI and p-value will be provided.

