1.5. Determination of Sample Size

The sample size for Cohorts 1 and 2 are based on safety and PK considerations.

The sample size for Cohort 3 is based on a 2-sample t-test assuming an improvement in DAS28-CRP change from baseline (CFB) for the KPL-404 being 1.2 points better than placebo (KPL-404 group CFB improvement = 2.2 points, placebo group CFB improvement = 1.0 point, standard deviation = 1.3). With 21 subjects in each of the 3 treatment groups (KPL-404 5 mg/kg qwk, KPL-404 5 mg/kg q2wk, and placebo) having completed 12 weeks of DAS28-CRP assessments, there is 83% power for the treatment comparison of active vs. placebo with 2-sided 0.05 type 1 error. In order to maintain this level of power after accounting for an anticipated discontinuation rate of 16%, up to 25 subjects per treatment group and up to a total of 75 subjects would need to be enrolled in Cohort 3.

The sample size for Cohort 4 is based on a 2-sample t-test assuming an improvement in DAS28-CRP change from baseline for the KPL-404 being 1.3 points better than placebo (improvement for placebo = 1.0 point, standard deviation = 1.3). Enrollment of 22 subjects into the KPL-404 arm and 14 subjects into the placebo arm (i.e., 3:2 randomization ratio) allows 80% power for the treatment comparison with 2-sided 0.05 type 1 error if all subjects complete 12 weeks of DAS28-CRP assessments. In order to account for an anticipated discontinuation rate of 10%, approximately 24 subjects (KPL-404) and 16 subjects (placebo) for a total of approximately 40 subjects are required to enroll under Cohort 4.

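### The sensitivity MMRM fixes one baseline slope and one stratum effect across visits, so its Week 12 difference departs by chance from the primary ANCOVA even with complete data (minor, cheap to fix)

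*SAP*

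**What the plan says.** SAP 4.6.2 makes the primary analysis an ANCOVA of change in DAS28-CRP at Week 12: "Baseline value and stratification factor will be included as covariates in the ANCOVA model". Only Week 12 outcomes enter, so both coefficients are Week 12 coefficients.

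The same section adds an as-observed sensitivity analysis, whose stated aim is "to evaluate the robustness of the primary analysis results with respect to the method of handling data" after treatment discontinuation or rescue. It keeps post-event data, imputes nothing, and fits an MMRM with unstructured covariance and Kenward-Roger degrees of freedom: "The MMRM model will include fixed factors for treatment, visit, stratification factor, and treatment-by-visit interaction, and baseline DAS28-CRP as a covariate". Treatment may interact with visit; baseline and stratum may not. No other section adds those terms.

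Section 4.6.2 does not list the visits in the MMRM. Weeks 2, 4, 8 and 12 are inferred from SAP Table 2 and the schedules of activities.

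**The concern.** A sensitivity analysis is easiest to read when it changes only what it is meant to test. Here the covariate adjustment changes as well, and the SAP gives no reason for that.

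If the slope of change on baseline differs between early visits and Week 12, the common slope is not the Week 12 slope. The Week 12 contrast is then adjusted for baseline differently from the primary analysis, and the same holds for the stratum effect. With 14 to 25 subjects per arm, some baseline imbalance is practically certain.

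What is at stake is interpretation. Part of any gap between the primary and sensitivity estimates would have nothing to do with discontinuation, rescue or missing data.

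**Working it through.** **Inputs from SAP 1.5.** Cohort 3: "KPL-404 group CFB improvement = 2.2 points, placebo group CFB improvement = 1.0 point, standard deviation = 1.3", "With 21 subjects in each of the 3 treatment groups", and, "accounting for an anticipated discontinuation rate of 16%, up to 25 subjects per treatment group". Cohort 4: difference 1.3, SD 1.3, 22 v 14 completers, 10% discontinuation, 24 v 16 enrolled.

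**The plan's own figures.** The two-sample t-test (noncentral t) gives 83.1% for Cohort 3, against "there is 83% power for the treatment comparison of active vs. placebo with 2-sided 0.05 type 1 error". Cohort 4 gives 81.1% against the stated 80%. Enrolment: 21/(1 − 0.16) = 25 per arm; 36/(1 − 0.10) = 40. All reproduce. The documents give no figure for an MMRM-versus-ANCOVA gap.

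**Identity.** Take complete data, with both models fitted to the same arms. Let Δy, Δx and Δz be the arm differences in mean Week 12 change, mean baseline and stratum proportion. Treatment-by-visit leaves each arm's mean free at each visit, so

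- ANCOVA difference = Δy − b12·Δx − s12·Δz
- planned MMRM difference = Δy − bc·Δx − sc·Δz
- gap (MMRM − ANCOVA) = (b12 − bc)·Δx + (s12 − sc)·Δz

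Here b12 and s12 are the fitted Week 12 coefficients, and bc and sc the fitted common ones. This step needs no assumption about slopes. Randomization gives Δx and Δz mean zero, so the gap averages zero. With both interactions every visit has the same regressors, the unstructured fit reduces to visit-by-visit least squares, and the gap vanishes.

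**Hand illustration (assumed values).** Take baseline SD 1.0, a Week 12 slope of −0.50 and a fitted common slope of −0.16 to −0.23, so the slope difference is 0.27 to 0.34 in size. A one-SE baseline imbalance is 1.0 × √(2/21) = 0.31 in Cohort 3 and 1.0 × √(1/22 + 1/14) = 0.34 in Cohort 4. The shift is 0.31 × 0.27 to 0.34 = 0.08 to 0.11, and 0.34 × 0.27 to 0.34 = 0.09 to 0.12 points.

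**Simulation, complete data, no intercurrent events.** There were 1000 data sets per scenario, with REML MMRM on four visits. Assumptions not in the documents: baseline SD 0.9; residual correlation 0.8 per visit lag; SD of change rising to 1.3 at Week 12; half the subjects in each stratum. Three patterns were used:

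- equal: slope −0.4 throughout, stratum effect 0.2
- moderate: slope −0.1 to −0.4, stratum effect 0.1 to 0.4
- steep: slope −0.1 to −0.7, stratum effect 0 to 0.6

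Each pair below is stratum balanced / not balanced by randomization.

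| Cohort, n | Pattern | SD of gap | 95th percentile of absolute gap |
|---|---|---|---|
| 3, 25 per arm | equal | 0.04 / 0.05 | 0.08 / 0.11 |
| | moderate | 0.08 / 0.10 | 0.16 / 0.20 |
| | steep | 0.14 / 0.17 | 0.29 / 0.33 |
| 3, 21 per arm | equal | 0.04 / 0.06 | 0.10 / 0.13 |
| | moderate | 0.10 / 0.11 | 0.21 / 0.23 |
| | steep | 0.16 / 0.19 | 0.31 / 0.35 |
| 4, 24 v 16 | equal | 0.06 / 0.09 | 0.13 / 0.20 |
| | moderate | 0.10 / 0.12 | 0.22 / 0.26 |
| | steep | 0.16 / 0.20 | 0.34 / 0.41 |

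A second set of assumptions (baseline SD 1.0, slopes −0.21 to −0.50) gave SDs of 0.11 to 0.13 in Cohort 3 (21 per arm) and 0.13 to 0.15 in Cohort 4 (22 v 14). With nearly equal slopes the SD was 0.04 to 0.07.

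Other results from the tabulated runs:

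- Mean gap: within 0.01 of zero throughout.
- Null rejection (Cohort 3, 25 per arm): 4.8% for ANCOVA, 5.1 to 5.3% for the planned MMRM.
- Disagreement on p < 0.05 with a true effect: 1 to 9% of data sets.
- Mean SE (Cohort 3, 25 per arm), ANCOVA v planned MMRM: 0.349–0.351 v 0.357–0.358 (moderate); 0.313 v 0.348–0.350 (steep).
- Both interactions added: estimates agree to about 1e-14 and SEs to about 1e-10 in every data set.
- Baseline-by-visit only: the 95th-percentile gap is 0.01–0.03 with a balanced stratum and 0.08–0.21 without.

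**The case against.** The strongest reply is that neither analysis is wrong. Main-effect covariates are a defensible, parsimonious choice in a small MMRM, and this is a sensitivity analysis in a phase 2 study with nominal p-values and no multiplicity control. An SD of 0.10 is about 0.10/0.35 = 29% of one standard error and under a tenth of the assumed effect. Every size above rests on slopes, correlations and a baseline SD that the documents do not supply. All of this stands, and it is why the point is minor.

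Three stronger readings might be inferred, and the documents support none of them:

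- *The planned MMRM is biased or inflates type I error.* It does neither. In a given trial the under-adjusted part follows the observed baseline imbalance, but over randomizations the gap averages zero.
- *The artefact is as large as the data-handling effect.* A simulation with 10 to 16% events and half the effect lost afterwards gave similar SDs for the two gaps (0.10–0.14 from the covariate constraint, 0.10–0.13 from data handling). That compares random spread. A sensitivity analysis looks for a systematic shift, and the result depends on the assumed loss and slopes.
- *With the interactions added, any remaining gap measures discontinuation and rescue handling alone.* It does not. The primary pairs a hypothetical strategy with LOCF, and the sensitivity analysis pairs treatment policy with MAR, so strategy and missing-data method still change together.

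The stratum-by-visit term adds little where randomization balances the stratum. It matters mainly for subjects randomized under Protocol Amendment 3, who were stratified on a different factor (SAP 4.2.2).

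**Conclusion.** The point holds as a minor specification weakness. The planned MMRM does not reproduce the primary ANCOVA's Week 12 covariate adjustment, so it adds a source of discrepancy unrelated to its stated purpose. That inequality follows from the model as written, whenever the fitted coefficients differ and the arms are not exactly balanced.

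Its size is conditional. Under the assumed slopes and stratum effects, the SD is about 0.04 to 0.17 points in Cohort 3 at 25 per arm (up to 0.19 at 21). In Cohort 4 it is about 0.04 to 0.15 under most assumptions and up to 0.20 under the steepest. Those are modest beside effects of 1.2 and 1.3, but a 95th percentile of 0.2 to 0.4 is enough to confuse a reading of the sensitivity result. Precision also suffers if the slope steepens over time: in the steep pattern the SE is 0.350/0.313, about 12% larger. The primary analysis is not in question.

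**What to change.** In SAP 4.6.2, give the MMRM these fixed effects: treatment, visit, treatment-by-visit, baseline DAS28-CRP, baseline DAS28-CRP-by-visit, stratification factor, and stratification factor-by-visit. Keep the unstructured covariance and Kenward-Roger. List the visits (Weeks 2, 4, 8 and 12, if that is the intention).

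The Week 12 adjustment then matches the primary ANCOVA. Any remaining gap reflects the joint change in intercurrent-event strategy and missing-data method (LOCF versus MAR), and the report should describe it that way.

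Cost: one sentence and six extra parameters (three per interaction over four visits), with no new data and no protocol amendment. If the slopes are really equal or change little, the SE is about 1 to 3% wider; in the equal-slope runs it was, for example, 0.356 v 0.352 in Cohort 3 (25 per arm) and 0.408 v 0.399 in Cohort 4, both with the stratum not balanced.

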4.6.3. Analyses of Secondary Efficacy Endpoints

[figure not shown]
The primary estimand for secondary efficacy endpoints is defined in Table 1, using the hypothetical strategy.

The intercurrent event is treatment discontinuation or using any rescue medications. Data will be set to missing values after occurrence of any intercurrent event prior to Week 12, and the subject's last post baseline observation before the intercurrent event will be carried forward

(LOCF) to impute missing endpoint value for all 7 ACR components (for subjects whose postbaseline values are all missing, the baseline will be used to impute). Missing data at Week 12 will be imputed with LOCF method. Responder status will be determined using the imputed components. However, subjects who discontinue treatment due to lack of efficacy will be considered as non-responders for all time points beyond the time of treatment discontinuation.

The analyses will use Cochran-Mantel- Haenszel (CMH) test adjusted by stratification factor. Response rate difference adjusted to stratification factors between each KPL-404 dose group and placebo will be derived. In addition, odds ratio and the corresponding 95% CI will be provided along with the p-values. If one or more expected cell frequencies are small (less than five), the CMH test may not be valid. In such cases, an exact CMH test will be performed instead.

In addition, logistic regression models may be used including key baseline characteristics as covariates along with the treatment groups.

4.7. Safety Analyses

All safety analyses will be conducted by treatment group in the Safety population for clinical and laboratory parameters, vital sign, and for adverse events (AEs). Adverse events will be coded using MedDRA of the version at database lock. Laboratory parameters, vital signs, and ECG data will be summarized as descriptive statistics by treatment, visit, and study period.

4.7.1. Adverse Events

Adverse events will be mapped to PT and SOC using the most up to date MedDRA of the version at database lock. A treatment-emergent AE (TEAE) is defined as any event not present before exposure to study drug or any event already present that worsens in either intensity or frequency after exposure to study drug during treatment period. Furthermore, if an AE cannot be determined as treatment-emergent due to incomplete/missing date, conservatively, it will be considered as treatment emergent and included in the summary tables. A post-treatment AE is defined as any AE that occurs during the off-treatment period (see the definition of treatment duration in Section 4.5).

The following TEAE summaries will be summarized by treatment group.

- Any TEAEs
- Drug-related TEAEs
- TEAE by maximum severity (mild, moderate, severe)
- Serious TEAEs (SAEs)
- Drug related serious TEAEs
- TEAEs leading to dose interruption
- TEAEs leading to treatment discontinuation
- TEAEs leading to study discontinuation
- Death
- TEAEs of special interest (AESI)

A subject experiencing the same AE multiple times will be counted only once for that preferred term. Similarly, if a subject experiences multiple AEs (preferred terms) within the same system organ class, then that subject will be counted only once for that system organ class. When summarizing by severity and relationship, only the event with highest severity or relationship will be counted. All AEs will be presented by SOC and preferred terms.

In addition, post-treatment AEs and SAEs will also be summarized.

All AEs will be displayed in by-subject listings.

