10.6.1.3. Adverse Events of Special Interest

An AE of special interest (AESI) is one of scientific and medical interest specific to understanding of the investigational product and requires close monitoring and communication by the Investigator with the Sponsor or designee within 24 hours of knowledge of the event, regardless of seriousness criteria. The rapid reporting of AESIs allows ongoing analysis of these events in order to characterize and understand them in association with the use of this investigational product. AESIs for the purposes of this study are as follows: thrombosis, serious infection, serious and non-serious bacterial infections, eye disorders, and anaphylaxis/hypersensitivity reactions. Anaphylaxis is defined below in Table 2 using Sampson's criteria (Sampson 2006).

Table 2: Clinical Criteria for Diagnosing Anaphylaxis

Ana	aphyl	axis is highly likely when any one of the following 3 criteria are fulfilled:
1.		tte onset of an illness (minutes to several hours) with involvement of the skin, mucosal tissue, or both generalized hives, pruritus or flushing, swollen lips-tongue-uvula)
	ANI	O AT LEAST ONE OF THE FOLLOWING:
	a.	Respiratory compromise (eg, dyspnea, wheeze-bronchospasm, stridor, reduced PEF, hypoxemia)
	b.	Reduced BP or associated symptoms of end-organ dysfunction (eg, hypotonia [collapse], syncope, incontinence)
2.		o or more of the following that occur rapidly after exposure to a likely allergen for that patient (minutes everal hours):
	a.	Involvement of the skin-mucosal tissue (eg, generalized hives, itch-flush, swollen lips-tongue-uvula)
	b.	Respiratory compromise (eg, dyspnea, wheeze-bronchospasm, stridor, reduced PEF, hypoxemia)
	c.	Reduced BP or associated symptoms (eg, hypotonia [collapse], syncope, incontinence)
	d.	Persistent gastrointestinal symptoms (eg, crampy abdominal pain, vomiting)
3.	Red	uced BP after exposure to known allergen for that patient (minutes to several hours):
	a.	Infants and children: low systolic BP (age specific) or greater than 30% decrease in systolic BP*
	b.	Adults: systolic BP of less than 90 mm Hg or greater than 30% decrease from that person's baseline
	1	I .

PEF, peak expiratory flow; BP, blood pressure.

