10.9. Recording Adverse Events

Adverse events spontaneously reported by the subject and/or in response to an open question from the study personnel or revealed by observation will be recorded during the study at the investigational site. Clinically significant changes in laboratory values, blood pressure, and pulse need to be reported as Aes. Abnormal values that constitute an SAE or lead to discontinuation of administration of study drug must be reported and recorded as an AE.

Adverse event collection will begin after the signing of the ICF. An adverse event that occurs prior to study treatment administration should be recorded in the eCRF only if it is an SAE or is an AE related to a study procedure. All Aes/SAEs that occur after the first administration of study treatment through the EOS visit, whether or not they are related to the study, must be recorded in the eCRF.

For subjects who terminate study participation early (i.e., before the Week 24 visit), the Investigator will report any SAEs that are reported to the Investigator within 30-day post-last dose administration.

Every reasonable effort will be made to follow subjects who have Aes/SAEs. Any subject who has an ongoing AE will be followed until resolution or the EOS visit.

The AE term should be reported in standard medical terminology when possible. For each AE, the Investigator will evaluate and report the onset (date and time), resolution (date and time), intensity, causality, action taken, serious outcome (if applicable), and whether or not it caused the subject to discontinue the study.

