11.7. Analysis of Safety

Descriptive statistics and changes from baseline, as applicable, will be calculated for safety parameters. No inferential statistical analyses are planned. The details regarding analyses will be provided in the SAP. Additional exploratory and post hoc analyses of the data may be conducted as deemed appropriate.

Analysis of TEAEs, defined as AEs that start or increase in severity after the first dose of study drug during treatment period, will be coded to system organ class and preferred term using the latest version of MedDRA. Analysis of post-treatment AEs, defined as any AEs that occur during the off-treatment period, will also be summarized in a similar manner.

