4.5. Treatment Exposure and Compliance

The study medication administration details including the administration date and time, dose, and comments will be presented in a by-subject listing.

The following parameters related to study drug administration will be summarized with descriptive statistics by treatment group for the safety population:

- Treatment duration in weeks is defined as [(minimum of (date of last study drug +13, EOS) Day 1 + 1/7] for Cohorts 1 and 2
- Treatment duration in weeks is defined as below for Cohort 3:

- 5 mg/kg SC qwk group: [(minimum of (date of last study drug +6, EOS) Day 1 + 1)/7]
- o 5 mg/kg SC q2wk group:
 - If the last dose is 5 mg/kg, then [(minimum of (date of last study drug +13, EOS) Day 1 + 1)/7]
 - If the last dose is placebo, then [(minimum of (date of last study drug +6, EOS) Day 1 + 1)/7]
- O Placebo group: [(minimum of (date of last study drug +6, EOS) Day 1 + 1)/7]
- Treatment duration in weeks is defined as [(minimum of (date of last study drug +27, EOS) Day 1 + 1)/7] for Cohort 4
- Number of dose administrations (injections) received per subject will be summarized as 1 dose, 2 doses, 3 doses, 4 doses, 5 doses and 6 doses for Cohorts 1 and 2, up to 12 doses for Cohort 3, and up to 3 doses for Cohort 4. Treatment compliance is defined as the number of injections that the subject is actually received divided by the total number of injections that the subject is planned to take from the first injection of study medications up to the actual last injection of study medications. No imputation will be made for subjects with missing or incomplete data.

All study drug exposure data will be listed including reasons for dose not administered.

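### The visible SAP 4.7.1 summarises AESIs only as treatment-emergent events, closing at nominal Day 84 or earlier, and names no AESI table from first dose to Week 24

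*SAP*

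**What the plan says.** SAP 4.7.1 gives ten summaries of TEAEs by treatment group. The last is "TEAEs of special interest (AESI", and it is the only AESI summary in the visible SAP. SAP 4.7.1 and Protocol 11.7 both confine TEAEs to the treatment period.

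SAP 4.7.1 sets the boundary by cross-reference: "A post-treatment AE is defined as any AE that occurs during the off-treatment period (see the definition of treatment duration in Section 4.5". SAP 4.5 defines treatment duration by regimen. For weekly dosing in Cohort 3 it reads "5 mg/kg SC qwk group: [(minimum of (date of last study drug +6, EOS) Day 1 + 1)/7" (with a minus sign before Day 1). The extension after the last dose is:

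- 6 days for Cohort 3 weekly dosing, for Cohort 3 placebo, and for Cohort 3 q2wk when the last injection was placebo
- 13 days for Cohorts 1 and 2, and for Cohort 3 q2wk when the last injection was active
- 27 days for Cohort 4

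For events after the boundary, SAP 4.7.1 says "In addition, post-treatment AEs and SAEs will also be summarized" and plans by-subject listings of all AEs. SAP 4.7 adds "All safety analyses will be conducted by treatment group in the Safety population". Protocol 11.7 says "Analysis of post-treatment AEs, defined as any AEs that occur during the off-treatment period, will also be summarized in a similar manner". None of these sentences mentions AESIs.

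Collection runs longer than the TEAE window. Protocol 10.9 requires recording of events "that occur after the first administration of study treatment through the EOS visit", and Protocol 7.3 asks subjects who stop treatment to keep attending visits through Week 24. The AESI definition in Protocol 10.6.1.3 has no time limit.

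**The concern.** The trial has a 12-week safety follow-up, and the protocol itself expects the drug to act into it. Protocol 4.3.1 reports full CD40 occupancy through Day 43 after one 5 mg/kg SC dose in healthy subjects. Protocol 8.2.1 asks for a wait of at least 4 months after the last dose for complete washout before a COVID vaccine. An AESI count by arm that stops at the TEAE boundary therefore leaves out time when an effect of the drug is still plausible.

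The post-treatment tables do not fully replace it, for two reasons.

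- **Grouping.** The AESI categories (thrombosis, serious infections, bacterial infections of any seriousness, eye disorders, and hypersensitivity including anaphylaxis) are not rows of a SOC/PT table.
- **Counting.** A subject with an AESI in each period is counted once in each table, so adding the tables counts that subject twice.

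To report how many subjects per arm had an AESI during the study, someone would have to rebuild the figure from listings.

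**Working it through.** **Inputs.** The Schedules of Activities put the last planned dose at Week 10 (Day 71) in Cohorts 1 and 2, Week 11 (Day 78) in Cohort 3 and Week 8 (Day 57) in Cohort 4. Week 24/EOS is Day 169. The extensions of 6, 13 and 27 days are from SAP 4.5.

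**Formula (SAP 4.5).** End of window = the earlier of (last dose + extension) and EOS. Duration in weeks = (end − Day 1 + 1)/7.

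| Group | End for a completer | Duration |
|---|---|---|
| Cohorts 1 and 2 | 71 + 13 = 84 | 84/7 = 12.0 weeks |
| Cohort 3 weekly, and placebo | 78 + 6 = 84 | 12.0 weeks |
| Cohort 3 q2wk, Week 11 injection placebo | 78 + 6 = 84 | 12.0 weeks |
| Cohort 4 | 57 + 27 = 84 | 12.0 weeks |

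This reproduces the plan's 12-week treatment period. Day 84 is not printed in the SAP; it follows for subjects dosed on schedule. The ±2-day visit window makes it Day 82 to 86. The q2wk row assumes active drug on Day 1; if the Week 11 injection were active, the end would be 78 + 13 = 91. Reading the treatment period as ending at the Week 12 visit (Day 85) moves the cut by one day.

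**Time left out, completers.** 169 − 84 = 85 days; 85/169 = 50.3% of the collected period.

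**Subjects who stop early.**

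- Cohort 3 weekly, one dose: 1 + 6 = Day 7
- Cohort 3 q2wk, one active dose: 1 + 13 = Day 14
- Cohort 3 weekly, last dose at Week 4: 29 + 6 = Day 35
- Cohort 4, loading dose only: 1 + 27 = Day 28
- Cohort 4, last dose at Week 4: 29 + 27 = Day 56

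The planned 16% discontinuation in Cohort 3 is 0.16 × 25 = 4 subjects per arm. The documents do not say when they would stop.

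**Drug effect past the cut (illustration).** Full occupancy through Day 43 after a Day 1 dose is 42 days.

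- *After one active 5 mg/kg dose:* 43 − 7 = 36 days past the cut (weekly) and 43 − 14 = 29 days (q2wk). This needs no multiple-dose projection, but still carries healthy-subject data over to RA patients.
- *Completers, assuming 42 days after the last active dose:* weekly 78 + 42 − 84 = 36 days; q2wk and Cohort 2 71 + 42 − 84 = 29 days; Cohort 4 at 80 kg 57 + 42 − 84 = 15 days.
- *Cohort 4 at 140 kg:* 400/140 = 2.86 mg/kg. Interpolating between the 1 mg/kg result (through Day 9, so 8 days) and the 5 mg/kg result (42 days): linear, 8 + 34 × 1.86/4 = 23.8 days; on log dose, 8 + 34 × ln(2.86)/ln(5) = 30.2 days. Less the 27-day extension, that is −3.2 (so 0) to 3.2 days. Below 80 kg the overhang is more than 15 days.
- *Cohort 1:* no 2 mg/kg single-dose result is given, so no figure.

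**Washout.** Taking 4 months as 120 days: 57 + 120 = 177, 71 + 120 = 191, 78 + 120 = 198. All fall after Day 169.

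**The case against.** The strongest reply is that nothing is lost. Late events are recorded, summarised by arm as post-treatment AEs and SAEs, and listed by subject. At about 25 subjects per arm in Cohort 3 and 24 and 16 in Cohort 4, an AESI subtotal can be rebuilt by hand. No safety inference is planned, so no test or estimate changes. Separating treatment-period from post-treatment events is a coherent choice, since background therapy may change after Day 85. Thromboembolic events, product-related anaphylaxis and severe infections are themselves reasons to stop treatment, so many such events will fall before the cut. All of this stands and keeps the point small. It does not supply a grouped count with each subject counted once.

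A reader might go further in four ways that the documents do not support.

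- **Late AESIs go unreported.** They do not, given the post-treatment summaries and listings.
- **The SAP breaches Protocol 10.6.1.3.** That section describes rapid reporting as allowing "ongoing analysis of these events in order to characterize and understand them in association with the use of this investigational product". It concerns 24-hour reporting during the trial and does not require a whole-study table.
- **No such table is planned anywhere.** The SAP of the Safety Review Committee is a separate document, SAP 4.8 and 4.10 are blacked out, and Protocol 11.7 neither names nor excludes a post-treatment AESI breakdown. Its wording on similarity follows a sentence about SOC/PT coding, so coding is the natural reading. Even a separate post-treatment AESI line would not give a combined count.
- **The 36, 29 and 15 days measure missed AESIs.** They are occupancy projections. For completers they ignore the roughly 3-fold accumulation in Protocol 4.3.1, which would lengthen them.

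**Conclusion.** The point holds for the visible SAP. The one AESI summary it names covers nominal Days 1 to 84 of the 169 collected for a completer, and as little as Days 1 to 7 for a weekly-dosed subject who stops after one dose. Drug effect is expected past that cut. Later AESIs are shown by arm, but not by AESI category and not in a form that counts each subject once over the study.

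This rests on the cross-reference from SAP 4.7.1 to 4.5 setting the TEAE boundary, on dosing to schedule for the Day 84 figure, and on active drug on Day 1 in the q2wk arm. A few late events with undeterminable onset dates may still enter the TEAE table, because SAP 4.7.1 classes them as treatment-emergent. How many AESIs would fall after the cut cannot be estimated from the documents. It is a worthwhile, optional improvement to safety reporting; neither the primary analysis nor data collection is in question.

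**What to change.** Keep the TEAE summary of AESIs. Add one table to SAP 4.7.1: number and percentage of subjects with any AESI, and with each category in Protocol 10.6.1.3, by treatment group, from first dose through Week 24. Show treatment period, follow-up and the combined period in separate columns, with each subject counted once per column. The AESI list, TEAE definition and reporting rules stay unchanged.

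The cost is one extra table from data already collected. Follow-up events are harder to attribute, because Protocol 8.2 allows csDMARD and corticosteroid changes after Day 85. The period split keeps that visible, and a footnote should say so.
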